In this Non-Intervention Study (NIS) all participating patients will receive standard routine care for breast cancer and information material with general background information on breast cancer, endocrine treatment, coping with the diagnose and lifestyle in order to enhance compliance [22]. This NIS aims to assess incidence and characteristics of arthralgias as a therapy-limiting and compliance-limiting side-effect, and assesses whether the incidence and severity of arthralgias is different in upfront anastrozole therapy and in anastrozole therapy following two to three years of tamoxifen treatment. Furthermore, compliance will be assessed and compared in patients experiencing arthralgias and patients not experiencing arthralgias. Arthralgia incidence and characteristics will be correlated to patient's compliance, and factors influencing arthralgias and compliance will be identified. Arthralgia characteristics will be particularly assessed using a validated VAS scale (Appendices E and F). Subjective perception of side-effects will be evaluated by psycho-oncologic scales (Appendices E and F). Costs of arthralgia therapy, as well as all costs of breast cancer therapy will be assessed and described in a descriptive manner. This study is part of a cooperation project with the GWQ (an organization including currently 19 sick funds). For patients who are insured in one of these sick funds and who consented to transfer of pre-defined data, study data will be compared to and validated by sick fund data.

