3. OBJECTIVES

Objectives:

Primary objective:

Assessment of arthralgia scores and patients` compliance within the first year of anastrozole treatment¹, stratified by upfront and switch therapy as well as assessment of the relationship between compliance and arthralgia scores.

Secondary objectives

Incidence of arthralgias and arthralgia characteristics within the first year of anastrozole therapy¹ stratified by upfront and switch therapy and assessment of the relationship of arthralgia incidence and arthralgia characteristics to patients` compliance.

Retrospective assessment of incidence of pre-existing arthralgias before start of anastrozole treatment, stratified by upfront and switch therapy.

Descriptive assessment of arthralgia therapy and of costs of arthralgia therapy, stratified by upfront and switch therapy.

The assessment of compliance and of arthralgia therapy will be compared to and validated by the corresponding data obtained by the sick funds of the patients.²

Assessment of subjective perception of side-effects by the patients, stratified by upfront and switch therapy.

Identification of factors influencing and correlating to treatment-emergent arthralgias, such as patient's characteristics (e.g. age, BMI), disease characteristics, duration of anastrozole treatment, subjective perception of side-effects by the patients etc.

Identification of factors influencing and correlating to patients' compliance; for example patient's characteristics (age), disease characteristics, concomitant medication, subjective perception of side-effects by the patients, incidence and characteristics of arthralgias (time between start of anastrozole therapy and occurrence, intensity and duration of arthralgias), incidence of AEs etc.

Compare time to progression (TTP) between patients with arthralgias and patients without arthralgias in the first year of anastrozole treatment, stratified by upfront and switch therapy.

Assessment of safety and tolerability of anastrozole.

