6. PATIENT SELECTION AND PLANNED NUMBER OF PATIENTS

Patients are eligible for inclusion in this NIS if they have taken anastrozole either upfront or following two to three years of tamoxifen treatment (“switch”) for at least three and not more than six months prior to offering an individual participation in this program. Treatment should follow local therapy guidelines and standard practice. Treatment decisions for patients participating in this study including assessments or supportive therapy during follow-up visits will also follow guidelines and remain independent of the program.

The patient population will include postmenopausal women with hormone-receptor positive primary breast cancer scheduled for adjuvant upfront endocrine treatment with anastrozole or following two to three years of tamoxifen treatment (“switch”) according to the current SmPC (Appendix C). Patients will have taken anastrozole for at least three months and not more than six months before the start of the study.

It is planned to enrol and document 3212 patients in this NIS. Further details regarding the objectives and the sample size consideration can be found in Section 3 and 11.5..

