7. PROGRAM PLAN AND PROCEDURES

7.1 Overall design and flow chart

This is an open, multicentre NIS.

[figure not shown]
It is planned to enrol subjects into this NIS between Q1 2009 and Q1 2010. Based on the plan outlined below, it is assumed that the last subject will be enrolled in Q1 2010 and subsequently documented until Q4 2010.

The treatment with anastrozole can be stopped at any time.

Furthermore it is expected, that the last completed eCRF will be filled in Q4 2010. It is planned to close all centres until end of Q1 2011 (i.e. the fees for all participating centres are paid).

Treatment with Anastrozole

Study duration

*or at point of treatment discontinuation

Evaluation period

Information to patients: study start, weeks 1, 3, 5, 8, 12, 20

- 1 The start of the adjuvant treatment with anastrozole is defined by the date of the first tablet intake. If this date is not available, the date of first prescription will be taken.
- 2 The end of participation in this NIS is defined as recurrence or death or withdrawal of informed consent is documented via WBDC. Patients who stop endocrine therapy (i.e. do not take further treatment) or patients who switch to an adjuvant endocrine therapy with tamoxifen or a different aromatase inhibitor or patients considered 'lost to follow-up' (i.e.: can no longer be contacted) will be documented as premature terminations. Otherwise this NIS terminates after completion of 12 (15) months observation period (12 respectively 15 months observation period results from time slot for inclusion, minimum 3 and maximum 6 months of anastrozole therapy prior to enrolment)

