7.6 Discontinuation of patients from program

Patients may discontinue participation in this program at any time. Specific reasons for discontinuing a patient from this program are:

- Withdrawal of informed consent
- Breast cancer recurrence
- Stop of adjuvant endocrine treatment (no further continuation of adjuvant treatment at all) or switch to an adjuvant endocrine treatment with tamoxifen or a different aromatase inhibitor

Patients should always be asked about the reason(s) for their discontinuation and the presence of any adverse events. For these cases, the investigator has to complete the consent withdrawal form and the respective forms in the eCRFs.

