Treatment discontinuation – Module (discontinuation of anastrozole therapy)	
Treatment compliance: doctor's assessment	Estimation of compliance by doctor's judgement: "How many tables have been taken in the observed period?" (none, few, less than half, appr. half, more than half, almost all, all)
Questions on arthralgias and	assessment of arthralgia occurrence during therapy with

related costs	
anastrozole (no, yes, unknown - if yes : localisation, swelling, pain intensity: mild/moderate/severe; duration, relationship to study drug: certain, probable, possible, unlikely, not related; serious: yes/no) Therapy of arthralgias: no, yes – please specify.
 
Assessment of treatment with medication (drug name, dose, package size, duration (start-end))
 
Action in concern of the therapy with anastrozol
 
Outcome
 
Relationship to anastrozole therapy, and treatment with medication
 
A reason to discontinue the therapy with anastrozol? SAE?

Discontinuation of treatment with anastrozole	
Date of last intake, unknown
 
Reasons for discontinuation (recurrence, death, patient's wish, physician's recommendation and specification of reasons, other, interactions with concomitant medication, AE – worsening of a concomitant disease: (hot flushes, headache, joint pain/arthritis complains (fingers, hands, arm, shoulder/ feet, knees, hip / spine), other)
 
AE – new: (hot flushes, headache, joint pain/arthritis complains (fingers, hands, arm, shoulder/ feet, knees, hip / spine), other)

Continuation of other endocrine treatment	
(no)
 
(yes – change of endocrine therapy which drug: tamoxifen, letrozole, exemestane, other - specification)

Switch – Module (continuation of endocrine therapy with tamoxifen or a different aromatase inhibitor)	
Continuation of other endocrine treatment	
(no)
 
(yes – change of endocrine therapy which drug: tamoxifen, letrozole, exemestane, other - specification)

Discontinuation of treatment	
Date of last intake, unknown
 
Reasons for discontinuation (recurrence, death, patient's wish, physician's recommendation and specification of reasons, other, interactions with concomitant medication, AE – worsening of a concomitant disease: (hot flushes,

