The assessment of compliance and of arthralgia therapy will be compared to and validated by the corresponding data obtained by the sick funds of the patients.²

For the subgroup of patients who consented to the data transfer of her sick funds data related to compliance and arthralgia therapy will be analyzed for correlation to the transferred data and described descriptively with standard statistics.

Assessment of subjective perception of side-effects by the patients, stratified by upfront and switch therapy.

Scores of GASE-P and SASS will be evaluated by presenting number and percentage of each category stratified by upfront and switch therapy. Groups will be compared using chi-square test.

Identification of factors influencing and correlating to treatment-emergent arthralgias, such as patient's characteristics (e.g. age, BMI), disease characteristics, duration of anastrozole treatment, subjective perception of side-effects by the patients etc.

Patient characteristics, disease characteristics and duration of anastrozole treatment will be described descriptively stratified by the occurrence of treatment-emergent arthralgias. A possible influence will be analyzed using logistic regression.

Identification of factors influencing and correlating to patients' compliance; for example patient's characteristics (age), disease characteristics, concomitant medication, subjective perception of side-effects by the patients, incidence and characteristics of arthralgias (time between start of anastrozole therapy and occurrence, intensity and duration of arthralgias), incidence of AEs etc.

Evaluation will be performed in the same way as described for the previous criterion.

Compare time to progression (TTP) between patients with arthralgias and patients without arthralgias in the first year of anastrozole treatment, stratified by upfront and switch therapy.

Time between start of anastrozole therapy and progression of disease will be analysed using the Kaplan-Meier method comparing patients with arthralgias to patients without arthralgias and upfront therapy to switch therapy.

Assessment of safety and tolerability of anastrozole.

The safety analysis will be descriptive and comprise all documented adverse events.

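### Regressing arthralgia on duration of anastrozole treatment can give an odds ratio on either side of 1 when risk does not change with exposure

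*Protocol*

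**What the plan says.** Protocol Section 3 lists the candidate factors for treatment-emergent arthralgia, among them "disease characteristics, duration of anastrozole treatment, subjective perception of side-effects by the patients etc". Section 11.4.1 repeats the objective and gives the analysis in two steps. The first is a descriptive comparison: "Patient characteristics, disease characteristics and duration of anastrozole treatment will be described descriptively stratified by the occurrence of treatment-emergent arthralgias". The second is the model: "A possible influence will be analyzed using logistic regression". This part of the section does not limit duration to the time before onset, does not use person-time and does not define who is at risk.

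Other sections bear on how duration and arthralgia are linked:

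- Section 1.3 describes the aim as assessing "incidence and characteristics of arthralgias as a therapy-limiting and compliance-limiting side-effect".
- The discontinuation module in Section 8.1.3 asks whether the arthralgia was "A reason to discontinue the therapy with anastrozol", and joint pain is among the listed reasons for stopping.
- Section 7.6 makes stopping endocrine treatment, or switching to another agent, a reason for leaving the programme.
- Under Section 6, women join after taking anastrozole "for at least three and not more than six months prior to offering an individual participation in this program".
- Section 7.1 explains that the "12 respectively 15 months observation period results from time slot for inclusion".

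**The concern.** Two mechanisms link duration to arthralgia without any effect of exposure on risk.

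First, the outcome can shorten the covariate. A woman whose arthralgia starts in month 4 and who stops for it in month 7 enters the model as a case with 7 months of treatment. A woman without arthralgia who completes the study enters as a non-case with 12 to 15 months. This pushes the odds ratio below 1, as if longer treatment protected.

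Second, the covariate sets the time in which the outcome can be seen. A woman treated and observed for longer has more months in which to report a first arthralgia. This pushes the odds ratio above 1, as if longer treatment harmed.

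The fitted coefficient mixes the two. Its sign and size then depend on how often arthralgia leads to stopping, how often women stop for other reasons, and when arthralgia starts. At stake is whether a named factor in a secondary objective is reported as influencing arthralgia when it does not.

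**Working it through.** **1. The plan's own figures.** The protocol gives no figure for this regression. Section 11.5 is used only to set a realistic number of women. Its 1119 per group (44% against 50%, two-sided 5%, 80% power, continuity-corrected) reproduces exactly, and its 394 per group for the t-test comes out at 393. 2 × 1119 / 0.70 rounds up to 3198, within 0.4% of the stated 3212. Evaluable women: 3212 × 0.70 = 2248.

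**2. Time to report, on its own.** Assume a constant arthralgia hazard, so that duration has no effect on risk. As a working value, take a 12-month risk of 35.6%. This borrows the joint-disorder figure in Section 1.1, which belongs to 68 months' median follow-up, so it is an assumption and is varied in step 4.

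- Hazard: h = −ln(1 − 0.356) / 12 = 0.0367 per month.
- Chance of arthralgia within D months: P(D) = 1 − exp(−hD).
- P(12) = 35.6%, odds 0.356 / 0.644 = 0.553.
- P(15) = 42.3%, odds 0.423 / 0.577 = 0.733.
- Odds ratio: 0.733 / 0.553 = 1.33 per 3 months, or 1.33^(1/3) = 1.10 per month.

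The 12-to-15-month spread among completers alone therefore gives an odds ratio above 1 with no exposure effect.

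**3. Adding treatment stops.** Simulation settings: 2248 evaluable women, entry uniform over 3–6 months on drug, 9 months of follow-up, and the constant hazard of step 2. A given share of women with arthralgia stop for it, a mean of 3 months after onset. Other stopping is independent. Only women still on treatment at entry are kept. Arthralgia (yes/no) is regressed on total duration, with 300 runs per row. The stopping shares are assumptions; the 23% borrows the tamoxifen non-compliance figure in Section 1.3 as an upper anchor.

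| Stop because of arthralgia | Other stopping by 12 months | Odds ratio per month | Nominal rejection at 5% |
|---|---|---|---|
| 0% | 10% | 1.121 | 99% |
| 10% | 23% | 1.056 | 81% |
| 20% | 10% | 0.929 | 91% |
| 30% | 10% | 0.876 | 100% |
| 50% | 10% | 0.794 | 100% |

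The null value is 1. Per 3 months, the first and last rows are 1.121³ = 1.41 and 0.794³ = 0.50. A second simulation used 8% unrelated stopping per year and a mean lag of 2 months. It gave 1.40, 1.12, 0.95, 0.73 and 0.61 per 3 months for arthralgia-driven stopping of 0, 5, 10, 20 and 30%.

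**4. Range over the unknowns.** With 12-month risk 20–50%, arthralgia-driven stopping 0–50% and other stopping 5–23%, still under a constant hazard, the odds ratio per month ran from 0.72 to 1.14 at 9-month follow-up. At the 3-month analysis it ran from 0.78 to 1.19. If onset is concentrated early (mean 2 months), it is about 1.00–1.03 when nobody stops for arthralgia and below 1 otherwise.

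**5. Does the alternative recover the null?** In the five scenarios of the table, a monthly Poisson hazard model was fitted with time on treatment as the axis. Women free of arthralgia were at risk from study entry only. The rate ratio was 0.999–1.001 per month, with rejection of 3–6%. Starting risk time at the first tablet, without allowing for delayed entry, left rate ratios of 1.000–1.031 and rejection rising from 4% to 93% as arthralgia-driven stopping rose from 0 to 50%.

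**The case against.** The strongest reply is that little depends on this estimate. It is one covariate in one secondary objective, and Section 11.1 makes all p-values descriptive and exploratory. Section 11.4.1 already describes arthralgia over exposure time by three-month intervals and by Kaplan-Meier, and Section 11.4 leaves details to the SAP. The limited stakes stand. The rest does not remove the bias. An exploratory label changes how a p-value is read, not where the estimate is centred. The Kaplan-Meier analysis serves the incidence objective. The protocol itself names the covariate and the model, so a SAP that follows it inherits the problem.

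A second reply is that duration might mean time on drug at entry, since the start date is recorded at registration. The text does not say so. On that reading the reverse path and the change of sign largely disappear, but the time-to-report bias remains: odds ratio 1.07–1.10 per month, with rejection of 28–46%.

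Two stronger readings are tempting. A reader might infer that arthralgia always ends treatment; the discontinuation module shows only that it can. A reader might also infer that the adjusted effects of age, BMI and the other factors are distorted. Section 11.4.1 does not say that all factors enter one joint model. When a covariate with hazard ratio 1.3 was added to the second simulation, its odds ratio with and without duration in the model was 1.393 against 1.391 at no arthralgia-driven stopping, and 1.381 against 1.388 at 30%. No material distortion was shown.

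**Conclusion.** The point holds for the duration estimate and should be corrected. As written, the analysis can report longer treatment as protective or as harmful when risk does not change with exposure. Both mechanisms follow from the protocol's own text. The direction and size do not: they rest on the assumed arthralgia risk, stopping shares, lag to stopping and onset pattern, and the range of 0.72 to 1.14 per month is conditional on those choices and on a constant hazard. With early onset and no arthralgia-driven stopping there is little bias. Neither the primary results nor the sample size is affected.

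**What to change.** In Section 11.4.1, remove total duration of anastrozole treatment as a covariate for treatment-emergent arthralgia. Describe the influence of exposure time by the rate of first arthralgia. Use time since first tablet as the time axis and count risk time only from study entry (delayed entry), among women still on anastrozole and still free of treatment-emergent arthralgia. Fit the other candidate factors in that interval or Cox model. Report arthralgias recalled from before entry separately and descriptively, noting that women who stopped before the 3–6 month entry window could not enrol. Align the factor list in Section 3 and the synopsis.

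No new data are needed. The start date is taken at registration and the date of last intake in the discontinuation module, and onset time is already required for the planned intervals and Kaplan-Meier analysis. The cost is slightly more analysis work, and events before entry do not contribute to the hazard model.

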The patient population will include postmenopausal women with hormone-receptor positive primary breast cancer receiving adjuvant endocrine treatment with anastrozole upfront or following two to three years of tamoxifen therapy (“switch”) according to the current SmPC (Appendix C). Patients will have received anastrozole treatment for at least 3 months and up to 6 months before the start of the study.

Randomisation

- No randomisation will be performed in this study.

Outcome variables

Compliance:

Compliance is defined by the percentage number of patients being ‘compliant’ to anastrozole therapy, based on the following information collected by the doctor at 0, 3, 6 and 9 months after study start:

- 1) Question about the daily intake of anastrozole (to be answered by the investigator):

”The patient was instructed to take 1 anastrozole tablet per day. However, it’s still possible that the intake has sometimes been forgotten. How many tablets, according to your impression of the patient, has the patient actually taken during the last year?”

Scoring:	0 – none	0%
	1 – few	[0% ; 20%]

2 – less than half	[20% ; 40%]
3 – approximately half	[40% ; 60%]
4 – more than half	[60% ; 80%]
5 – almost all	[80% ; 100%]
6 – all	100%.

- 2) Question about the daily intake of anastrozole (to be answered by the patient in the patient questionnaire)

”You were instructed to take 1 anastrozole tablet per day. However, it’s still possible that the intake has sometimes been forgotten. How many tablets have you actually taken during the last year?”

Scoring:

0 – none	0%
1 – few	[0% ; 20%]
2 – less than half	[20% ; 40%]
3 – approximately half	[40% ; 60%]
4 – more than half	[60% ; 80%]
5 – almost all	[80% ; 100%]
6 – all	100%.

- 3) A patient will only be defined as being ‘compliant’ when the answer of the doctor **and** the patient score ‘5’ or ‘6’ concerning the question regarding the number of tablets actually taken.

Arthralgias

Arthralgias will be summarized by incidence, localization, onset, duration, intensity, and relationship to study drug, diagnostics and arthralgia management (e.g. medication, physiotherapy, doctor’s visits, change of life style etc.). Arthralgia characteristics will be particularly assessed using VAS scores (Appendices E and F).

Perception of side-effects

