The ITT analysis set will be used for the primary analysis of compliance and arthralgia scores. The safety population(s) will be the basis for the analysis of costs and safety analyses and for a secondary analysis of arthralgia scores. Additionally, all women who completed this NIS and who were compliant according to the criteria defined in the protocol for the total duration of 12 months of anastrozole treatment will be analysed separately with regard to the arthralgia characteristics (VAS score, incidence, intensity etc), side-effect management, related costs, perception of side effects etc.

¹ The start of the adjuvant treatment with anastrozole is defined by the date of the first tablet intake. If this date is not assessible, the date of the first prescription of anastrozole can be used instead.

² This is only applicable to patients who consented to data transfer and who are insured by sick funds who joined the respective contract. Data transferred from the sick funds will include breast-cancer related costs from 12 months before study start up to the end of the study for the respective patient.

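### Time to progression is compared between groups defined by arthralgia arising after time zero, so immortal time makes arthralgia look protective; late entry separately makes every curve too favourable

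*Protocol*

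**What the plan says.** Section 3 lists as a secondary objective: "Compare time to progression (TTP) between patients with arthralgias and patients without arthralgias in the first year of anastrozole treatment". The comparison is to be made within the upfront and switch strata. Section 11.4.1 gives the method: the interval from starting anastrozole to progression "will be analysed using the Kaplan-Meier method comparing patients with arthralgias to patients without arthralgias". The upfront and switch groups are contrasted in the same way. The footnote to that section fixes time zero: "The start of the adjuvant treatment with anastrozole is defined by the date of the first tablet intake", with the first prescription as fallback.

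Two design features matter here. Section 6 states: "Patients will have taken anastrozole for at least three months and not more than six months before the start of the study". Section 7.1, footnote 2, states: "The end of participation in this NIS is defined as recurrence or death" (or withdrawal of consent), and otherwise sets the end at 12 to 15 months after treatment start, that is, nine months after study start.

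No landmark, time-dependent grouping or late entry into the risk set is stated. Section 11.1 says that all p-values are read in a descriptive-exploratory way.

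**The concern.** Membership of the arthralgia group is settled by something that happens after the clock has started. A woman whose joint pain begins after study entry can be classed as having arthralgia only if she stayed recurrence-free until it began. One who recurs first leaves observation and stays in the other group for good. Recurrences are thus moved from one group to the other by the definition alone.

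The second problem is distinct. Nobody can be seen to recur in the study before entry, yet Kaplan-Meier from first tablet counts those 3 to 6 months as time at risk.

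Section 1.1 describes joint symptoms as limiting compliance and as a barrier to prescribing. A spurious finding that arthralgia goes with fewer recurrences would bear directly on the study's own subject, and the upfront and switch curves would both look better than they are.

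**Working it through.** The protocol states no event count, hazard ratio or power for TTP, so there is no planned figure to reproduce. The check asks what the stated analysis returns when arthralgia and progression are unrelated (true ratio 1).

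**Inputs from the protocol:** clock from first tablet; entry at 3 to 6 months; nine months of observation after entry; observation ends at recurrence; 3212 women; 30% drop-out.

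**Assumptions not in the protocol:** constant progression hazard; entry uniform over months 3 to 6; arthralgia in a share p = 20%, 35.6% or 50% of women by month 12 (35.6% is the joint-disorder figure for anastrozole in section 1.1, at 68 months' median follow-up, and is only a guide); onset either uniform over 0 to 12 months, or early (exponential with mean 3 months, truncated at 12).

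**1. Approximation for rare events.** Let A be the onset month and E the entry month. Let m be the mean of max(A − E, 0), the recurrence-free wait after entry among women who would develop arthralgia. Of their nine observed months, recurrences in m months are credited to the other group. Time from first tablet is nearly the same for both groups and cancels, as does the hazard:

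ratio ≈ (9 − m) / (9 + m·p/(1 − p))

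- Uniform onset: m = mean of (12 − E)²/24 = (7.5² + 0.75)/24 = 2.375.
- Early onset: m = [3(e⁻¹ − e⁻² − e⁻⁴) − 7.5e⁻⁴]/(1 − e⁻⁴) = 0.515.

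| p | Uniform onset | Simulated | Early onset | Simulated |
|---|---|---|---|---|
| 20% | 6.625/9.594 = 0.69 | 0.69 | 8.485/9.129 = 0.93 | 0.92 |
| 35.6% | 6.625/10.313 = 0.64 | 0.63 | 8.485/9.285 = 0.91 | 0.92 |
| 50% | 6.625/11.375 = 0.58 | 0.58 | 8.485/9.515 = 0.89 | 0.89 |

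The simulated columns use 4,000,000 women per setting, 3% progression per year and no drop-out; 30% drop-out changes them by at most about 0.015. At 2% per year the simulated ratios are 0.58 to 0.71 with onset spread over the year and 0.90 to 0.94 with early onset.

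**2. Do the repairs work?** In the same simulations at 3% per year, a time-dependent arthralgia state with entry at study start gives 0.98 to 1.01. A landmark at study entry gives 0.97 to 1.01.

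**3. Does late entry cause the contrast?** No. Applying left truncation while keeping the fixed groups leaves the ratio at 0.629 (largest change in any setting 0.001). If women were followed for 12 months from the first tablet, m would be the mean of A itself. For uniform onset at 35.6%, that gives (12 − 6)/(12 + 0.553 × 6) = 6/15.317 = 0.39 (simulated 0.40), further from 1 than 0.63. For early onset the simulated ratio is 0.68 without late entry against 0.92 with it.

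**4. What late entry does distort.** On the first-tablet clock, the apparent hazard is zero to month 3, rises in line with the share entered to month 6, and is correct afterwards. Hazard counted to month 12: 3 × ½ + 6 = 7.5 of 12 months, or 62.5%. The simulations agree: 1.26% against 2.0% at 2% per year, and about 1.9% against 3.0% at 3% per year.

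**5. Chance of a false result.** In 500 simulated studies of 3212 women per setting (35.6% arthralgia, with and without 30% drop-out), a nominal two-sided 5% comparison pointed falsely to protection as follows; 2.5% is expected in that direction.

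| Progression per year | Uniform onset | Early onset |
|---|---|---|
| 1% | 13–15% | about 4% |
| 3% | 30–38% | 4–6% |
| 5% | 49–59% | about 6% |

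**The case against.** Four arguments limit the point.

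- **Late entry.** A reader might infer that it adds to the protective look. It does not: the event-free months before entry are shared by both groups, and arthralgia present at entry carries no differential immortal time. Late entry could bias the contrast only if entry depended on both arthralgia and progression risk, on which the protocol gives no figures.
- **Size.** A reader might take a single figure near 0.65 to 0.7 as the expected bias. That holds only if much of the arthralgia starts after entry. With early onset the ratio is about 0.9. Section 11.4.1 also says treatment-emergent arthralgia for the risk-factor analysis but plain arthralgia for TTP; if pre-existing joint pain counts, the bias shrinks further.
- **Certainty.** Events are few (about 60 to 72 at 3% per year), so in most settings a study would not reach nominal significance. The direction of the bias is certain; a significant false finding is not.
- **Status.** TTP is secondary, has no event target, and its p-values are exploratory. Section 11.4 leaves details to an SAP that is not shown.

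All four stand as limits, but none removes the defect. The protocol itself fixes estimator, origin and groups, so an SAP that follows it inherits the bias and one that corrects it departs from the protocol. An exploratory label does not remove a bias of known direction.

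**Conclusion.** The arthralgia comparison of TTP is wrong as written. Immortal time pulls the hazard ratio below 1 when there is no relation: to about 0.6 if onset is spread over the first year, and to about 0.9 if most of it precedes study entry. The range rests on assumed onset timing, arthralgia frequency and a constant recurrence hazard; the direction does not depend on which of the tested values is used.

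As a separate matter, all TTP curves on the first-tablet clock, including upfront against switch, show about 63% of the true 12-month recurrence under a constant hazard with entry uniform over months 3 to 6. This is an error in level and is not a source of the protective contrast.

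Grade: should be fixed. The secondary, descriptive-exploratory status of TTP does not support a higher one.

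**What to change.** In section 11.4.1, replace the TTP comparison with one of the following:

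- **Landmark:** group women by arthralgia status known at study start, count time from study start, and stratify by upfront and switch therapy. This alone removes the bias.
- **Alternative, where onset dates allow:** a Cox model stratified by upfront and switch, with arthralgia as a time-dependent covariate and women entering the risk set at study start.

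For any curve kept on the first-tablet clock, including upfront against switch, let women enter the risk set at study start (left truncation). State whether arthralgia that predates anastrozole counts.

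The cost is wording, best settled before the first database lock. The protocol already collects the anastrozole start date (8.1.1), arthralgia since treatment start at baseline (8.1.2), recurrence date (8.1.3) and adverse event start date (8.3.1.2).

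There are small downsides. The landmark ignores arthralgia that starts after entry. The time-dependent model relies on recalled onset for arthralgia before entry, and the follow-up patient questionnaire (8.2.2) asks only whether arthralgia occurred in the past three months, so onset dates must come from the investigator's record.
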